## **5.0 Number of Subjects**

Two nursing homes will be recruited for comparison of LSB with care as usual. A power analyses for a MANOVA, with 2 groups and 2 dependent variables, was conducted in G\*Power Version 3.1.9.2 [32] to determine a sufficient sample size. Using an alpha ( $\alpha$ ) of .05, and a large effect size of  $d = .94$  [33], a sample size of 20 could achieve a power of 95% to detect between group differences.

Prior research in long-term care facilities indicates that oversampling by 15-20 percent is an efficient way to deal with attrition. This study will recruit 24 residents, or 12 residents per NH, to ensure a sample size of 20. From these two NHs, a minimum of 20 NH residents (10 per NH) and a maximum of 24 NH residents (12 per NH) will be recruited.

**FULL PROTOCOL TITLE:** The Effectiveness of Life Story Book on Depression and Meaning in Life for Mentally Alert Residents of Nursing Homes

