**1.0 Objectives**

The purpose of this research is to test quantitatively the effectiveness of the Life Story Work (LSW) intervention, with a book product (LSB), for reducing depression and increasing meaning in life (MIL) for mentally alert nursing home (NH) residents.

The overall objective is to improve the quality of life for residents of NHs by determining whether the LSB intervention will have a greater and longer lasting effect compared with care as usual (i.e., decreased depression and increased meaning in life).

Hypothesis I LSB will lead to greater reductions in depressive symptoms than care as usual.

**FULL PROTOCOL TITLE:** The Effectiveness of Life Story Book on Depression and Meaning in Life for Mentally Alert Residents of Nursing Homes

Hypothesis II LSB will lead to a greater increase in MIL than care as usual.

My central hypothesis, formulated from my preliminary research, is that the LSB intervention will improve the quality of life for mentally alert NH residents and will have longer lasting effects than care as usual. If effective, it may offer a non-pharmacological intervention for improving care and quality of life for NH residents.

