**8.0      Study Timelines**

- (1) Eligibility screening – 10 minutes
- (1) Initial visit, consents, study overview and instruments   60-90 minutes
- (5) Intervention visits – 60-90 minutes
- (1) Potential visit for NH-B if any edits were required to their LSB   30-60 minutes

Total maximum time for participation after screening = 10 hours

**FULL PROTOCOL TITLE:** The Effectiveness of Life Story Book on Depression and Meaning in Life for Mentally Alert Residents of Nursing Homes

Immediately upon IRB approval, recruitment will begin and will continue until a minimum of 10 and a maximum of 12 from each NH are recruited (Total for both NHs- 20 minimum and 24 maximum). The intervention will begin as soon as recruitment levels are met. Transcription will begin after the first LSB visit and will continue until all LSBs are complete. The intervention will take 10 weeks to complete. At the conclusion of all data collection and transcription activities, data analyses will be conducted. We anticipate that that we will be able to conduct the intervention within four months following IRB approval. Primary analyses should be completed within six months following IRB approval. (*See attached timeline*).

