[name] is an Assistant Professor at the University of Houston College of Nursing and named a 2018 Salute to Nurses Top 15 winner. She has served as an oncology nurse for 37 years and is certified in gerontology. In addition, [name] is a certified instructor for Reminiscence and Life Story Work. She will serve as a consultant on this study.

The two NHs that will be recruited will be described upon their consent and letters of cooperation will be obtained. The NHs will be comparable on the following five aspects: number of long-stay residents, overall quality rating, staff rating, type of ownership (private, public or government) and facility size. Each of the NHs participating in this study will have a minimum of 85 residents. According to the Vital Statistics report- *Long-Term Care Services in the United States: 2013 Overview*, there are about 49.6% of NH residents who are mentally alert [3]. With approximately 50% of NH residents being mentally alert, there will be approximately 42 residents to recruit from the NHs that house 85 residents.

Two social work/medical professionals will be hired as research assistants. Once they are hired, I will submit an IRB modification with their information.

An IRB modification with the two site coordinators information, along with the nursing home letters of cooperation, will be added.

Recruitment will begin immediately upon IRB approval and will continue until the minimum of 10 and maximum of 12 participants from each NH (Total 20 minimum and 24 maximum) are recruited. Transcription will begin immediately after each LSB visit with participants and data will be analyzed after all data collection is complete. We anticipate that we will be able to complete the intervention three months following IRB approval. The LSB intervention and analyses should be completed within six months following IRB approval.

**FULL PROTOCOL TITLE:** The Effectiveness of Life Story Book on Depression and Meaning in Life for Mentally Alert Residents of Nursing Homes

Adequate psychological and/or medical resources are available and can be provided by the NHs for those who may need it as a result of an unanticipated consequence of research participation.

The research team will communicate on an ongoing weekly basis to discuss any issues that may arise so as to ensure successful execution of this research study. All of the key personnel listed in this study have read and understand this protocol.

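### The 95% power claimed for 20 residents does not follow from an effect labelled d = .94; it reproduces only if .94 is the multivariate effect size f²(V)

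*Combined protocol and SAP*

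**What the plan says.** Section 5.0 is the only justification of the sample size. It reports: "A power analyses for a MANOVA, with 2 groups and 2 dependent variables, was conducted in" G*Power, at alpha .05 with a large effect labelled d = .94 and attributed to a cited source. It concludes that "a sample size of 20 could achieve a power of 95% to detect between group differences". The 20 is a total, 10 per home. The section does not say which outcome the .94 belongs to, gives no correlation between outcomes, and shows neither software output nor a conversion of d into the input that the MANOVA routine needs.

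On attrition, 5.0 says that "oversampling by 15-20 percent is an efficient way to deal with attrition" and then "This study will recruit 24 residents, or 12 residents per NH, to ensure a sample size of 20". The next sentence, however, allows "a minimum of 20 NH residents (10 per NH) and a maximum of 24 NH residents (12 per NH) will be recruited". Section 8.0 ("recruitment will begin and will continue until a minimum of 10 and a maximum of 12 from each NH are recruited") and section 29.0 ("will continue until the minimum of 10 and maximum of 12 participants from each NH") repeat that minimum.

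The analysis in section 25.0 is a one-way MANCOVA on GDS-12R and MLQ with the pre-test scores as covariates. No pre-post correlation is stated anywhere.

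**The concern.** A single-outcome comparison of 10 against 10 at d = .94 has only about 51% power (two-sided t test, alpha .05). A jump to 95% from adding a second outcome is not credible without a special correlation structure, so the effect size was probably not on the d scale when the calculation was run.

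The statement misleads on either reading. If .94 is a d, a reader will take a null result as having had a 5% chance of missing that effect, when the chance in the unadjusted test is several times larger. If .94 is an f²(V), the power is right but applies to an effect about twice the size that the label conveys.

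**Working it through.** **Inputs.** From 5.0: two groups, two outcomes, alpha .05, effect .94, N = 20 in total (maximum 24), equal homes. Assumed, because the plan gives no values: the within-group correlation r between outcomes, both coded so that higher means benefit; which outcomes carry the effect; and the pre-post correlation rho.

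**Formula.** With two groups and two outcomes the MANOVA test is an F test with df1 = 2, df2 = N − 3 and noncentrality N × f²(V). For equal groups the noncentrality is also (N/4) × D², where D is the multivariate distance, so f²(V) = D²/4. In general D² = (d1² − 2·r·d1·d2 + d2²)/(1 − r²).

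**Step 1: reproduce 95%.** Put f²(V) = .94. At N = 20 the noncentrality is 20 × .94 = 18.8.
- N = 19: 93.9%
- N = 20: 95.2%

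Twenty is the smallest N that reaches 95%, which matches the plan. The implied distance is D = √(4 × .94) = √3.76 = 1.94 SD. If both outcomes share the effect equally, that is a d of 1.37 (r = 0) to 1.79 (r = .7) on each. Entering .94 as f, so that f² = .8836, gives 94.0% at N = 20 and needs 21 for 95%; that is not a d either.

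**Step 2: take .94 as a standardised difference.** d² = .8836.
- One outcome carries it: f²(V) = d²/[4(1 − r²)]. At r = 0 this is .8836/4 = .2209, and the noncentrality at N = 20 is 4.418.
- Both carry it: f²(V) = 2d²/[4(1 + r)]. At r = 0 this is 1.7672/4 = .4418, and the noncentrality at N = 20 is 8.836.

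Unadjusted power:

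| Pattern | N | r = 0 | r = .3 | r = .5 | r = .7 |
|---|---|---|---|---|---|
| One outcome | 20 | 38.8% | 42.2% | 49.8% | 67.1% |
| Both outcomes | 20 | 68.0% | 56.0% | 49.8% | 44.7% |
| One outcome | 24 | 46.9% | 50.8% | 59.3% | 77.0% |
| Both outcomes | 24 | 77.9% | 65.9% | 59.3% | 53.7% |

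These are not bounds. At N = 20, one outcome with r = .9 gives 98%, and both outcomes with r = −.3 give 84%. Simulation (40,000 runs) agreed with the N = 20 rows to within about half a point.

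**Step 3: the planned MANCOVA.** Simulated with equal homes and rho of .5 and .7:

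| Pattern | N | rho = .5 | rho = .7 |
|---|---|---|---|
| One outcome, r = 0 | 20 | 45% | 60% |
| Both, r = .5 | 20 | 57% | 74% |
| Both, r = .3 | 20 | 63% | 80% |
| One outcome, r = 0 | 24 | 54% | 72% |
| Both, r = .5 | 24 | 68% | 84% |
| Both, r = .3 | 24 | 74% | 89% |

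Favourable combinations do reach 95%. At N = 20: rho .7, one outcome, r = .8 (97%); rho .7, both, r = −.3 (97%); rho .5, one outcome, r = .9 (99%). At N = 24: rho .7, both, r = 0 (95%).

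**Step 4: the recruitment minimum.** If only 20 are recruited and loss matches the oversampling allowance (an assumption), 20/1.20 = 16.7 to 20/1.15 = 17.4 remain, about 17. Unadjusted power at N = 17 over the patterns of step 2 is 32% to 59%.

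**The case against.** **The source of .94 cannot be seen.** If it is an f²(V), the 95% is right and the defect is one wrong symbol. This stands: the documents cannot settle which reading applies, and the f²(V) entry is inferred from the match. What is certain is that label and power disagree.

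**The 39% to 68% range rests on assumptions, and its ends fit the protocol poorly.** Section 1.0 aims at "decreased depression and increased meaning in life", so both outcomes are expected to move, and section 2.0 treats meaning as protective against depression, which suggests an aligned correlation above zero. This is fair. With both outcomes and r of .3 to .7, the unadjusted figures are 45% to 56% at N = 20 and 54% to 66% at N = 24. That narrows the range but does not rescue 95%.

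**The planned analysis is a MANCOVA, which is more powerful when the pre-tests are informative.** This also stands, so the unadjusted miss rate should not be read as that of the planned analysis. But 5.0 powers a MANOVA, takes no credit for covariates and gives no pre-post correlation. Across the main adjusted scenarios in step 3, power stays at or below 80% at N = 20 and 89% at N = 24.

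**The remedy is only wording.** That is true, but the wording is the sole basis offered for the sample size.

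**Conclusion.** The concern holds. The stated 95% is not the power of the stated test at d = .94 and N = 20. On the d reading, the chance of missing the effect in the unadjusted MANOVA is about 32% to 61% for an assumed aligned correlation of 0 to .7, against the 5% implied. On the f²(V) reading, 95% is correct, but for a distance of about 1.94 SD.

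The result on the label is firm. The exact power on the d reading is not, because it depends on r, on which outcomes carry the effect and, for the MANCOVA, on rho. All figures treat residents as independent; with one home per arm, none allows for clustering.

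Separately, recruiting 24 to secure 20 and permitting a recruited total of 20 cannot both stand as worded, since a recruited total of 20 leaves no allowance for loss.

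**What to change.** In 5.0, state what .94 is, show the software input, and do one of the following.

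1. **If the cited .94 is an f²(V):** relabel it, and say that 95% at N = 20 applies to a multivariate distance of about 1.9 SD.
2. **If it is a d:** replace 95% with the power after conversion, using f²(V) = d²/[4(1 − r²)] when one outcome carries the effect or 2d²/[4(1 + r)] when both carry the same d. State r and the pattern assumed. Here r must be the within-group correlation after both outcomes are coded in the direction of benefit. If the raw scores run in opposite directions, entering a raw r of −.5 would give 94% and wrongly appear to confirm the claim. The coding should be explicit, because the MLQ anchors and the above-24 rule in section 10.0 point in different directions.

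If credit is taken for the pre-test covariates, also state rho, use about f²/(1 − rho²) with df2 = N − 5, and check by simulation; at N = 20 the formula was 4 to 6 points too optimistic. Give figures for both 20 and 24, and say that they treat residents as independent.

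For recruitment, soften the assurance in 5.0 that 20 will be retained, so that it agrees with the permitted minimum. Sections 8.0 and 29.0 can then stay as they are.

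The cost is a few sentences in 5.0. Enrolment limits, design and analysis do not change. The stated power, or the effect it applies to, becomes less favourable.

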### *Description of all research procedures being performed and when they are performed:*

After identifying potential participants, private informational meetings with the research team which will include the PI and two research assistants -will be conducted with each potential participant where initial screening, using the SIS, will be administered by the PI. (*Please see attached screening script/tool*). If the resident is eligible, and would like to participate, the research team will further explain the study, including the length of the study-10 weeks with six visits, length of the visits 1- hour, three weeks with no visits, and the measures that will be

**FULL PROTOCOL TITLE:** The Effectiveness of Life Story Book on Depression and Meaning in Life for Mentally Alert Residents of Nursing Homes

collected. Full disclosure and written consents will be explained with plenty of time for any questions or clarification before consent forms are signed. The consent form will include the purpose, procedures, risks and costs of participating in the LSB. Again, there will be no costs for participating in the study and the research team will receive no monetary income from the LSB. In addition, the LSB will be the property of the participant, along with any scanned photos or stories written. This will be signed by each participant, each RA, and the PI. A copy of the consent form will be given to each participant. Additional information will be provided for those participants who would like to request their family's cooperation to secure photos and/or memorabilia. (*See attached information sheet*).

Although the recruitment of participants is for mentally alert residents, if they have given durable power of attorney to others, it may be necessary, per their NH regulations, to obtain informed consent from their designated durable powers of attorney [35], [36], [37]. The durable power of attorney will be contacted, permission sought, and the consent form signed. The consent form will also include an agreement that the LSB ownership will be with the participant. [38] A copy of the consent form will be given to the durable power of attorney.

Participants will be notified for scheduling of the LSB intervention, by their preferred method of notification, once recruitment is completed. When participant recruitment levels are met, the research team will contact the participants to schedule their first visit. LSB visits for all participants will begin the same week.

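### The permitted recruitment floor of 20 carries no attrition margin, so the stated 95% power holds there only if nobody is lost

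*Combined protocol and SAP*

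**What the plan says.** Section 5 reports a G*Power calculation for a MANOVA with two groups and two outcomes, alpha .05 and an effect size of .94. It concludes that "a sample size of 20 could achieve a power of 95% to detect between group differences".

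It then says that "oversampling by 15-20 percent is an efficient way to deal with attrition" and draws the consequence: "This study will recruit 24 residents, or 12 residents per NH, to ensure a sample size of 20". In that sentence 20 is what should remain after losses, and 24 is what should be enrolled.

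The next sentence gives a range for enrolment itself: "a minimum of 20 NH residents (10 per NH) and a maximum of 24 NH residents (12 per NH) will be recruited". Two later sections repeat it as a stopping rule:

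- Section 8: "recruitment will begin and will continue until a minimum of 10 and a maximum of 12 from each NH are recruited", followed by "The intervention will begin as soon as recruitment levels are met".
- Section 29: recruitment "will continue until the minimum of 10 and maximum of 12 participants from each NH (Total 20 minimum and 24 maximum) are recruited".

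Section 10 (procedures) is written for the upper figure only: it refers to 24 participants at the first visit and gives each research assistant six participants per home. Section 16 foresees withdrawal by choice or for health reasons. Section 25 says that reasons for withdrawal and loss to follow-up will be recorded. No section describes replacing a lost participant or imputing missing outcomes.

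**The concern.** The same number, 20, serves first as the count to be left after attrition and then as the lowest count that may be enrolled. The floor cannot be read as a completer count, because sections 5, 8 and 29 all attach it to recruitment. If recruitment stops there, the oversampling that section 5 has just justified does not exist. Once the intervention starts, nothing in the plan restores it.

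What is at stake is how the power statement is read. A reader would take the 95% to cover any enrolment from 20 to 24. At the lower end it depends on complete retention, in a population for which the plan itself expects attrition. The text does not say so.

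**Working it through.** **Inputs.** From section 5: MANOVA global test, 2 groups, 2 outcomes, alpha .05, effect size .94, N = 20, power 95%, oversampling 15-20%, recruitment 20 to 24.

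**Step 1: reproduce the plan's figure.** With 2 groups and 2 outcomes, the global F test has df1 = 2 and df2 = N − 3, with noncentrality λ = N × f². Entering .94 as f² at N = 20 gives df2 = 17, λ = 20 × 0.94 = 18.8 and power 0.952. At N = 19, df2 = 16, λ = 17.86 and power is 0.939. So 20 is the smallest total that reaches 95%, and one loss from 20 goes below it.

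**Step 2: check the 24.** 20 × 1.15 = 23 and 20 × 1.20 = 24. The planned 24 agrees with the stated oversampling rate.

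**Step 3: completers.** The plan gives an oversampling rate, not a loss rate. Assumption: it reflects expected loss. It can be read in two ways.

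| Reading | Loss | Left from 20 | Left from 24 |
|---|---|---|---|
| Implied by oversampling: 3/23 to 4/24 | 13.0-16.7% | 17.4-16.7 | 20.9-20.0 |
| 15-20% taken directly as loss | 15-20% | 17.0-16.0 | 20.4-19.2 |

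The first reading leaves about 17 from a floor of 20. The figure of 16 arises only at the top of the second.

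**Step 4: power at those numbers** (same formula, f² = .94).

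| N analysed | Power |
|---|---|
| 24 | 0.983 |
| 20 | 0.952 |
| 19 | 0.939 |
| 18 | 0.923 |
| 17 | 0.903 |
| 16 | 0.878 |
| 14 | 0.811 |

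From 20 recruits, 16-17 completers give 0.88-0.90, a fall of about 5 to 7 points. From 24 recruits, 20% loss leaves about 19, with power about 0.94.

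**Step 5: timing.** The comparison between LSB and care as usual is made at the first post-test, which section 10 sets at 4 weeks for NH-B. If only half the loss has occurred by then (assumption: 6.5-10%), 20 recruits leave 18.7 to 18.0, and power is 0.92-0.94.

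**Step 6: the planned analysis.** Section 25 specifies a MANCOVA with pre-test scores as covariates. Assume that .94 is the unadjusted f², that both outcomes share one pre-post correlation r, and that two error degrees of freedom go to covariates. Then f² becomes .94/(1 − r²) and df2 becomes N − 5. At N = 17, power is 0.89 for r = 0, 0.92 for r = .3 and 0.96 for r = .5. The plan gives no value for r.

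**The case against.** A target with a lower acceptable number beside it is an ordinary feasibility device. Section 5 says plainly that 24 will be recruited, and section 10 is built on 24. The 24 is computed consistently. Section 5 claims only that 20 could achieve 95%, and with full retention it does. The shortfall under plausible loss is small: power stays above 0.80 down to 14 analysed, and covariate adjustment may recover all of it.

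Most of this stands, and it limits the point to a missing qualification. It does not remove it. The floor is nowhere described as a feasibility concession or as lacking the margin that the preceding sentences call for.

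Three stronger readings are tempting, and the documents do not support them:

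- *The 95% is simply wrong at the floor.* It is not: 20 analysed gives 0.952 on the calculation that reproduces the plan. The figure is conditional on no losses.
- *The attrition arithmetic is wrong.* It is not: 15-20% on top of 20 is 23-24.
- *The trial is seriously underpowered because of the floor.* Section 5 labels .94 as d, and a true d of .94 would give much lower power, but that would be so at 24 as well as at 20. It is a separate question about the effect-size input and lends no weight to this one.

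**Conclusion.** The point holds as a minor inconsistency in the sample-size statement. Sections 5, 8 and 29 permit recruitment to stop at the number that section 5 wants left after attrition, and no replacement is described. That conclusion rests on the text alone and needs no assumption about the loss rate.

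The size does rest on assumptions. If the oversampling rate reflects loss and .94 is used as f² in an unadjusted MANOVA, stopping at 20 leaves about 16-17 completers and power of about 0.88-0.90 against the stated 95%. If only half the loss precedes the first post-test, it is 0.92-0.94. Adjustment for pre-test scores could reduce or remove the shortfall, depending on a correlation that the plan does not give.

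**What to change.** **Preferred.** In sections 5, 8 and 29, make 24 (12 per home) the recruitment target, in line with section 10. Note that if loss reaches 20%, 24 leaves about 19 with power about 0.94, so the target restores the margin without guaranteeing 95%.

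**If a floor of 20 is kept for feasibility.** State beside it that it carries no attrition margin, that 95% power holds there only with no losses, and that power is about 88-90% at 16-17 completers. Mark these figures as subject to separate resolution of the effect-size label. Align section 10 with the range: refer to all participants rather than to 24, and to five or six per research assistant per home (20/2/2 = 5; 24/2/2 = 6).

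**Cost.** Wording only, since 24 is already the planned number. With 24 as the target, consented residents may wait for the twelfth volunteer in each home, because section 10 says that "LSB visits for all participants will begin the same week", and some could be lost meanwhile. Section 29 requires at least 85 residents per home, about 42 of them mentally alert. At that minimum size, twelve is 12/42 = 29% of the pool, against 10/42 = 24% for ten, and both shares rise after the English-speaking criterion and consent. Keeping a labelled floor costs only a less favourable power statement there.
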